2.2 Study Objectives and Endpoints

The overall objective of this study is to evaluate the efficacy, safety, and tolerability of StrataGraft when used as an overlay of meshed autograft to facilitate wound closure and reduce donor site harvest in the treatment of FT thermal burns.

The two comparative study treatment sites per subject are as follows:

- The study treatment that is StrataGraft Overlay of Meshed Autograft (SOMA), where meshed autograft is applied to the burn area and covered with StrataGraft and applied to a burn area, hereafter will be referred to as "SOMA Tx."
- The study treatment that is autograft alone as applied to a burn area hereafter will be called "AG Tx"

When collectively referring to both study treatments (i.e., the SOMA Tx and the comparator AG Tx), we will hereafter refer to "Study Tx."

2.2.1 Efficacy Primary Objective and Co-primary Endpoints

The primary efficacy objective is to evaluate the efficacy of SOMA treatment by assessing two co-primary efficacy endpoints. The definitions of the two co-primary efficacy endpoints are as follows:

- Calculated percent reduction of donor skin (as defined by [1-(AG Tx mesh ratio/SOMA Tx mesh ratio)× 100]) at Month 2.
- Difference in percent of SOMA Tx sites and AG Tx sites with confirmed complete wound closure without additional autografting at Month 2.
 - Confirmed complete wound closure is defined as complete skin reepithelialization without drainage confirmed at 2 visits at least 2 weeks apart but
 no later than Week 20. Complete wound closure will be considered to have
 occurred at the earlier of the two observations of complete skin reepithelialization without drainage.
 - Confirmed complete wound closure without additional autografting at Month 2 is determined by Mallinckrodt's biostatistics and programming team based on the above definition. The first wound closure needs to have occurred before Month 2.

2.2.2 Efficacy Secondary Objectives and the Secondary Efficacy Endpoints

The 2nd efficacy secondary objective is to evaluate the efficacy of SOMA Treatment by assessing the following 2nd efficacy endpoints:

- Incidence of confirmed complete wound closure of the study Tx sites at Days 14, 21, 28, and 42, Month 2, and Month 3.
- Percent re-epithelialization of the study Tx sites at Day 14, 21, 28, and 42, Month 2 and Month 3.
- Percent subjects with durable wound closure of study Tx sites at Months 3, 6, and 12.
 - Durable wound closure is defined as persistence of closure, maintained for at least 3 months after the initial observation of closure. The blinded assessor will evaluate the wound sites at each visit subsequent to wound closure to assess the maintenance of the closure.
- Patient and Observer Scar Assessment Scale/Patient Scar Assessment Questionnaire (POSAS/PSAQ) scores of Study Tx sites at Day 28, Months 2, 3, 6, and 12.

2.2.3 Efficacy Tertiary / Exploratory Objectives and Endpoints

The tertiary efficacy objective is to evaluate Health Care Resource Utilization (HCRU) and explore other efficacy endpoints.

Health Care Resource Utilization (HCRU) endpoints are defined as follows:

- Location of care for StrataGraft application (e.g., inpatient hospital, outpatient/ambulatory hospital, clinic, etc.).
- Treatments used for all other non-study burn areas following excision and % total body surface area (TBSA) treated with each (i.e., other than Study Tx sites).
- Number and duration of operating room procedures required for study burn treatment.
- Length of hospital stay.
- Prescription drugs given for pain control.
- Antibiotics given for outpatient use at discharge.
- Re-admission within 30 days after discharge.
- Whether a re-admission is planned.
- Length of hospital stay after re-admission.

The efficacy exploratory endpoints are as follows:

Confidential and Proprietary

- Calculated total area of autologous (donor) skin applied to study treatment sites by Month 6.
- Time to first confirmed complete wound closure without additional autograft by Month 2

2.2.4 Safety Objectives

The safety objective is to evaluate the safety of SOMA treatment. At the same time, the safety of control treatment, i.e., autograft, site will also be displayed for reference, where applicable. The safety measurements are as follows:

- Incidence of treatment-emergent AEs (TEAEs) throughout study.
- Incidence of TEAEs related to each of the Study Tx's.
- Incidence of wound infection-related events at Study Tx sites.
- Clinically significant changes in vital signs throughout study compared to Baseline.
- Clinically significant changes in laboratory values between Baseline and Day 28.
- Clinically significant changes in panel reactive antibodies (PRA) and anti-bovine serum albumin (BSA) levels between Baseline and Month 3.
- Concomitant medication use.

2.2.5 Additional Outcome Measures

- Number of treatment sites with complete wound closure without additional autografting at Month 2.
- Number of subjects with durable wound closure of the study treatment sites without additional autografting at Month 12.

2.2.6 Adverse Events of Special Interest

An Adverse Event of Special Interest (AESI), whether serious or nonserious, is one of scientific and medical concern specific to the sponsor's product or program, for which ongoing monitoring and rapid communication by the investigator to the sponsor can be appropriate. AESI will be reported using the SAE/AESI Report Form and observe the same reporting timeline (within 24)

hours of first knowledge of an event or receipt of follow up information). For this study, AESI include:

- Unexpected or unusual infections.
- Dermatological malignancy.

2.2.7 Modification from the Statistical Section of the Final Protocol

The amendments to the statistical section and relevant endpoints of the final protocol are displayed here. The final analyses are based on this final SAP. The amendments are as follows:

In protocol section 4, objectives and endpoints (p. 19):

The exploratory endpoint, "Effect of total wound burden on rate of wound closure," is listed. However, no data has been collected on overall donor site closures. Consequently, no analysis will be performed for this endpoint.

- The protocol does not mention the endpoint 'Time to First Confirmed Wound Closure
 Without Additional Autograft by Month 2.' (see Section 2.2.3) However, this endpoint and
 its results were outlined in the briefing document (see the References: Type B Meeting
 Briefing Materials submitted in IND 010113 Sequence 0151 on 27 November 2023),
 leading to its inclusion.
- In protocol section 10.3.2 Efficacy Analyses (p36):
 The original analyses for the first co-primary endpoint as stated in the clinical protocol were as follows:

For calculated percent reduction of donor skin (as defined by [1-(AG Tx mesh ratio/SOMA Tx mesh ratio) × 100]) at Month 2, the log-transformation of the endpoint will be performed, and geometric mean ratio percent reduction of donor skin between treatment site will be presented.

A mixed-effect model repeated measures method with covariates, including subject treatment site, mesh ratio on SOMA Tx site, and cohort will be used for this log-transformed primary endpoint.

If the mixed-effect model repeated measures model does not converge or violates the model assumptions, the paired t-test will be used. If parametric statistics models are not appropriate, the Wilcoxon signed-rank test will be performed.

The updated statistical analysis will not use log-transformation, to facilitate easier clinical interpretation. Additionally, the mixed-effect model for repeated measures will not be used due to the small number of subjects and the existence of only one cohort. To ensure robustness of the method, the non-parametric Wilcoxon signed-rank test, as originally planned last method, will be used (see Section 3.7.1).

2.3 Sample Size Considerations

The sample size for the study is based on clinical experience. No calculations were performed to estimate sample size. Up to 40 subjects will be enrolled in 2 cohorts (details in Section 2.1).

2.4 Randomization and Blinding

This is a randomized, open-label study.

There will be a total of 40 subjects enrolled in the study. On each subject, two wounds, comparable in area, wound bed composition (fat, fascia, or muscle), and kinesiologic stressors will be identified, designated as Sites A and B, and randomized to receive either AG Tx (control) or SOMA Tx, such that each subject receives both treatments.

There are two cohorts, as described in Section 2.1, based on the size of wound areas. Cohort 1 treatment sites are 100 to 400 cm², whereas Cohort 2 treatment sites are 400 to 1,900 cm².

2.5 Ad-hoc Data Review

Due to slow enrollment, the sponsor performed a preliminary assessment of the efficacy and safety of the product in April 2023 to determine the appropriateness of amending the ongoing Phase 1/2a StrataSOMA clinical study to a seamless Phase 1/2/3 study design. To this end, the sponsor performed an ad-hoc data analysis for the first 10 subjects enrolled in Cohort 1 after 1st 10 subjects completed primary endpoints assessments. Results of this data review were included

in Sponsor Meeting Materials for a Type B meeting with FDA to discuss the proposed clinical study amendment.

The ad-hoc data review demonstrated that all of the first 10 subjects enrolled in the StrataSOMA study achieved confirmed complete wound closure by or before Month 2 without additional autografting on both SOMA and AG treatment sites, regardless of whether they were randomized to the m+1 or m+2 group (i.e., 100% of the SOMA treatment sites achieved confirmed complete wound closure by or before Month 2 without additional autografting).

Additionally, SOMA treatment decreased the amount of donor tissue required to close treated sites relative to the control AG treatment site by 35% and 57% for autograft mesh ratios m+1 and m+2, respectively, without sacrificing cosmetic outcomes, as evidenced by comparable POSAS scores at Months 2 and 3.

For safety, ad hoc analyses of TEAEs or SAEs for the first 10 patients through the data cutoff showed that most TEAEs and SAEs were typical of what is observed in burn wounds and during wound healing. The safety profile at the StrataGraft treatment sites was similar to that of the control treatment sites, and no new safety signals were identified.

For details of the ad-hoc analyses, see the Type B Meeting Briefing Materials submitted in IND 010113 Sequence 0151 on 27 November 2023 (see References).

This ad-hoc data analysis will not alter the screened significance level of the entire study.

2.6 Pharmacokinetics

Pharmocokinetic parameters are not evaluated in this study.

2.7 Pharmacodynamics

Pharmacodynamic parameters are not evaluated in this study.

2.8 Pharmacoeconomics

Pharmacoeconomics parameters are not evaluated in this study.

3 STATISTICAL METHODS AND CONVENTIONS

3.1 General Conventions

- Unless otherwise noted, the number of subjects (n), mean, standard deviation, median, minimum, and maximum will be presented for continuous variables and frequency and percentage of subjects in each category will be presented for discrete variables.
- Unless otherwise noted, confidence intervals (CIs) will be 2-sided 95% CIs.
- Listings will be sorted by subject identification.
- Statistical analyses will be done using Statistical Analysis Software (SAS®) version 9.3 or higher.
- All statistical tests will be two-sided with a final significance level of 0.05, unless stated otherwise.

3.1.1 Handling of Missing Data

No imputation for missing values will be conducted. All observed values (i.e., excluding missing values for visit) will be used for the analyses except for the second co-primary endpoint, missing data will be imputed as non-responder.

3.1.2 Date/Time Derived Variable Conventions

Study Day 1 when Study Tx is applied will be considered as baseline for the endpoint calculations.

3.2 Analysis Populations

- All Enrolled Population.
- Full Analysis Set (FAS).
- Per-Protocol Set (PPS).
- Safety Analysis Set (SAF).

3.2.1 All Enrolled Population

The All Enrolled Population is defined as all subjects who signed the Informed Consent Form (ICF).

3.2.2 Full Analysis Set (FAS)

The Full Analysis Set is defined as all subjects who are randomized and treated with at least one area of SOMA Tx and one area of AG Tx. Efficacy analyses will be based on treatment applied (as treated).

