7.3. Method of Treatment Assignment

This study is designed as an open label, within-subject comparator study.

For randomization of Study Tx sites within each subject, an interactive voice randomization system will be used in this study and sites trained on its use.

For each subject, after excision/debridement is completed and the Study Tx sites are confirmed to meet Eligibility Criteria, comparable (ie, similar in both area and depth) Study Tx sites will be identified as A and B by the surgeon as outlined below:

- Treatment Site A will always be anterior, superior, proximal, lateral or to the subject's right
- Treatment Site B will always be posterior, inferior, distal, medial or to the subject's left

After anatomical assignment of Study Tx sites to Site A and Site B is completed per protocol definitions, Study Tx sites will be randomized to receive either:

1. Meshed autologous split-thickness skin graft (ie, AG Tx)
2. Meshed autograft overlaid with up to 1:1 mesh of StrataGraft (ie, SOMA Tx):
 - a. 1 mesh ratio greater than the control site

- b. 2 mesh ratios greater than the control site

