7.4. Blinding

This study will be open label for the investigators performing the care of enrolled subjects, including the application of the Study Tx. All wound assessments, however, will be performed by a previously designated blinded assessor.

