2 PROTOCOL SUMMARY

2.1 Study Design

This is a Phase 1/2a, multicenter, open-label, randomized, within-patient controlled study in subjects with 2% to 49% (inclusive) TBSA thermal burn. The overall objective of this study is to evaluate the efficacy, safety, and tolerability of StrataGraft as an overlay for meshed autograft to promote complete wound closure and reduce the area of donor site harvested in the treatment of FT thermal burns.

The targeted enrollment for this study is 40 subjects with FT thermal injury. On each subject, 2 wounds, comparable in area, wound bed composition (fat, fascia, or muscle), and kinesiologic stressors will be identified, designated as Sites A and B, and randomized to receive either AG Tx (control) or SOMA Tx, such that each subject receives both treatments. Following excision, the control autograft treatment site will receive meshed split-thickness skin graft, while the SOMA treatment site will receive autograft that is meshed at 1 or 2 mesh ratio(s) greater than the control treatment site and overlaid with StrataGraft meshed up to 1:1.

Cohort 1 will consist of 20 subjects randomized to one of 2 groups: Group 1 (n=10) will receive AG Tx consisting of autograft alone (mesh ratio "m", per clinical judgment) compared to SOMA Tx in which m+1:1 meshed autograft is overlaid with StrataGraft, while Group 2 (n=10) will receive AG Tx with autograft (mesh ratio "m" per clinical judgment) compared to SOMA Tx in which m+2:1 meshed autograft is overlaid with StrataGraft, applied to wounds of 100 to 400 cm² in area. Subjects will be followed and assessments performed per the Schedule of Activities (Table 1). Each subject will be determined to be a success or failure based upon the criteria below, and one of the 2 treatments, m+1 or m+2, will be determined to meet the *a priori* established criteria within the algorithm to move forward:

- Percent closed (re-epithelialization) at Day 28, with success declared if the difference between paired wounds < 10%.
- Total score of Observer assessment of the POSAS at Day 28, with success declared if the difference between paired wounds < 20%.

Cohort 2 will consist of 20 subjects, all of whom will receive the SOMA Tx (with autograft meshed at m+1 or m+2) identified following assessment of Cohort 1 and the AG Tx control, applied to wounds of 400 to 1,900 cm² in area. Subjects will be followed, and assessments performed per the Schedule of Activities (Table 1).

Advancement to Cohort 2

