Following excision, a total of 20 subjects (Cohort 1) will be randomized into one of 2 groups, Group 1 and Group 2.

Following completion of the Day 28 assessments, each subject will be determined to be a success or failure based upon the criteria below:

- % closed at Day 28, with success declared if the difference between paired wounds
 10%, and
- Total score of Observer assessment of the POSAS at Day 28, with success declared if the difference between paired wounds < 20%.

Group success will be declared if \geq 80% subjects are determined to have treatment success within that group. Only one of the 2 SOMA Txs, m+1 or m+2, will be determined to meet the *a priori* established criteria above and become the SOMA Tx in Cohort 2.

Treatment Groups and Duration:

This study is open-label. Subjects will serve as their own control. Subjects will be randomized to receive autograft, meshed at a ratio per clinician judgment at 1 treatment site (m), and StrataGraft overlay of autograft at either m+1 (i.e., group 1) or m+2 (group 2), relative to the control autograft mesh ratio.

It is anticipated that each subject will participate in this study for up to 14 months: up to 2 weeks of screening followed by up to 12 months (± 4 weeks) of post-treatment observation.

Estimated Duration of Study

Enrollment ~36 months.

Duration of subject participation up to 60 weeks.

Total study duration ~96 months.

Study Was Terminated Early by Sponsor

Study enrollment was terminated on 12 January 2024 due to a decision to voluntarily discontinue sale and manufacture of StrataGraft for business reasons. A total of 13 subjects were randomized, all in Cohort 1, at the time of termination of enrollment. Follow up for enrolled subjects was completed in April 2024.

Scientific Rationale for Study Design

The current standard of care for closure of FT burns is autografting, i.e., the surgical harvest of healthy skin from an uninjured site and subsequent transplantation of the donor tissue to the wound following surgical excision of nonviable tissue from the burn. While this method is effective in achieving closure of the original wound, optimal sites for the harvest of donor skin are often limited, and closure of large areas of injury may necessitate sequential re-harvest of available donor sites. Additionally, the donor site is painful, susceptible to infection and scarring,

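### Efficacy in the full analysis set is grouped by treatment applied with no analysis by randomized assignment; the effect is limited and arises only if a site or subject was treated other than as assigned

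*SAP*

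**What the plan says.** SAP 3.2.2 defines the FAS as "all subjects who are randomized and treated with at least one area of SOMA Tx and one area of AG Tx" and adds: "Efficacy analyses will be based on treatment applied (as treated". Protocol 10.2 uses the same rule, so the two documents agree.

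There are two randomizations. Protocol 7.3 covers the sites: "After anatomical assignment of Study Tx sites to Site A and Site B is completed per protocol definitions, Study Tx sites will be randomized" to AG or SOMA. SAP 2.1 covers the subjects: "Cohort 1 will consist of 20 subjects randomized to one of 2 groups", m+1 or m+2.

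Protocol 7.4 on masking: "This study will be open label for the investigators performing the care of enrolled subjects, including the application of the Study Tx". It continues: "All wound assessments, however, will be performed by a previously designated blinded assessor".

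SAP 3.7 summarizes efficacy by treatment site and by relative mesh group. SAP 3.7.1 states that there is no formal hypothesis test and that p-values are for signal exploration.

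**The concern.** Randomization makes the two sites, and the two mesh groups, comparable apart from chance. Analysis by treatment applied keeps that property only while assignment and application agree. If a surgeon who knows the assignment places the overlay on the other site, or meshes at the other step, the site or subject changes analysis group. The reason may be linked to how the wound was expected to heal. Blinded assessment protects the scoring of the outcome; it does not protect group membership.

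At stake is whether the SOMA versus AG and m+1 versus m+2 comparisons can be read as randomized comparisons if a departure occurred. A plan has to settle this in advance, because choosing between the two analyses after seeing the data is the weaker position.

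**Working it through.** The plan gives no sample size calculation, power or stated figure on this point, so there is nothing to reproduce. The check has two parts: whether anything else in the plan covers a departure, and how much one could matter.

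**1. Other provisions**

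- The per-protocol set (SAP 3.2.3) is a subset of the same as-treated FAS. Its open-ended list of deviations does not name treatment other than as assigned. Under SAP 3.7.1 the per-protocol analysis is dropped if the two sets differ by 2 subjects or fewer.
- SAP 3.6 summarizes allocated sites, mesh ratios and placement. It does not set assigned against applied treatment subject by subject.
- The control ratio is the clinician's choice (SAP 2.1). Neither document says that it must be recorded before the assignment is known.

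No analysis by randomized assignment appears in either document.

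**2. Month 2 closure (second co-primary)**

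Inputs: 13 subjects randomized, all in Cohort 1 (SAP 2.1). The first 10 all closed at both sites by Month 2 without further autografting (SAP 2.5). All 13 are assumed to be in the FAS.

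Let b be the pairs closed at SOMA only and c the pairs closed at AG only. The paired difference is (b − c)/13.

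- Relabelling a concordant pair changes it by 0.
- Relabelling a discordant pair moves one count between b and c, a change of 2/13 = 15.4 points.
- The first 10 pairs are concordant, so at most 3 pairs can contribute. In the extreme case all 3 are discordant in one direction and all are swapped: the difference goes from −3/13 = −23.1 to +23.1 points. The exact McNemar p-value is 2 × (1/2)³ = 0.25 either way.

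**3. Continuous paired endpoints**

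For re-epithelialization and the POSAS total score (paired t-tests, SAP 3.7.2), relabelling a pair with difference d moves the mean difference by 2d/13. For illustration, d = 10 points gives 20/13 = 1.5 points. The documents give no standard deviation, so the effect on the test cannot be stated. Any subject with a non-zero difference counts here, so all 13 are exposed. Re-epithelialization is exposed only until both sites close, because SAP 3.7.2 sets closed wounds to 100%. Time to closure by site (SAP 3.7.3.2) is exposed wherever the two sites closed at different times.

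**4. Mesh groups**

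The split of the 13 is not given. With an assumed 7 and 6, one subject is 1/7 = 14.3% or 1/6 = 16.7% of a group. Under the 80% rule for group success, moving one failing subject out of a group of 7 would change 5/7 = 71.4% to 5/6 = 83.3%. Cohort 2 never opened, so that rule no longer drives a decision.

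**5. Donor skin reduction (first co-primary)**

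The formula is read as 100 × (1 − AG ratio/SOMA ratio). Individual ratios are not given, so m = 2 is assumed.

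| Pair | Labels by treatment applied | Randomized labels, sites swapped |
|---|---|---|
| 2 and 3 | 100 × (1 − 2/3) = +33.3% | 100 × (1 − 3/2) = −50.0% |
| 2 and 4 | 100 × (1 − 2/4) = +50.0% | 100 × (1 − 4/2) = −100.0% |

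With 13 positive pairs the exact two-sided Wilcoxon p-value is 2/2¹³ = 0.00024. If swapped pairs carried randomized labels and took the largest ranks (an assumption), it would be 0.021 with 1 swap, 0.168 with 2 and 0.542 with 3. That change would come from the labels alone: the site with the wider mesh would be scored as having used more donor skin when it used less. For this endpoint the site label should follow the graft applied.

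**The case against.** The strongest case against runs as follows. No departure is reported. The trial is exploratory, and each FAS subject contributes both treatments, so pairs stay intact. The paired wounds must be matched on area, bed tissue and mechanical stress, and Sites A and B are labelled by a fixed anatomical rule. Randomization follows excision, so the surgeon has already seen the wound bed, and departing from assignment would be a protocol deviation. Deviations are adjudicated before database lock, and wound assessment is blinded.

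Most of this stands, and it limits the weight of the point. A reader might infer that randomization is the only safeguard against the better wound going to one treatment; matching, anatomical labelling and blinded assessment show otherwise. A reader might also infer that any of the 13 subjects could move Month 2 closure by 15.4 points; SAP 2.5 rules out the first 10.

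Two things do not fall. Adjudication decides who enters the per-protocol set, but it does not restore randomized groups. Exploratory status does not make the grouping unimportant either. SAP section 1 foresees use in regulatory submissions or manuscripts. SAP 2.5 reports that donor skin reductions of 35% (m+1) and 57% (m+2), with the closure results, went into materials for a regulatory meeting.

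**Conclusion.** The point holds in a limited form. Both documents fix an as-treated efficacy analysis and plan no analysis by randomized assignment. If any site or subject was treated other than as assigned, the comparison no longer follows the randomization. If none was, the two analyses are identical.

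The largest direct effect on a co-primary endpoint is 15.4 points in Month 2 closure per swapped discordant pair, possible only among 3 of 13 subjects. This assumes that all 13 are in the FAS and that the closure results reported for the first 10 stand at the final analysis. Re-epithelialization, POSAS and time to closure are exposed in all 13, by an amount the documents do not allow to be computed.

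A reader might infer that randomization was in fact broken, or that the donor skin result is fragile to swaps. The documents support neither. They record no departure. The donor skin endpoint is calculated from mesh ratios, and wound prognosis enters it only through later regrafting.

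**What to change.** In SAP 3.2.2, replace the as-treated sentence with the following rules, and record the change from protocol 10.2 in SAP 2.2.7:

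- Closure, re-epithelialization, POSAS and time to closure are analysed by randomized site.
- Summaries of m+1 versus m+2 are by randomized group.
- Donor skin reduction keeps site labels by the treatment actually applied, uses the recorded mesh ratios, and is reported by randomized mesh group.
- Every subject whose applied treatment differed from assignment is listed. If there are any, the as-treated results are given as a sensitivity analysis.

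The cost is a few sentences and one listing. An extra set of tables is needed only if a departure occurred. If none did, one line in the study report saying so closes the question.
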